1.0 Abstract

Etonogestrel Subdermal Implant (ESI) is an attractive alternative to other long-acting reversible contraception as well as a compliance-independent alternative to estrogen-containing hormonal contraception. Though its safety and efficacy has been established world-wide, only about 1% of women have been reported to use this method [6]. Its use and future expansion is limited by bleeding alterations which result in requests for early removal. Unfortunately, published data regarding bleeding changes and ESI in US women is limited. A multicenter trial of 330 US women reported a 13.0% removal rate for “bleeding pattern changes,” within the first 8 months of use [1], consistent with the results of an international trial [2]. We reported on a retrospective cohort of 155 US women and developed an algorithm that improved unacceptable bleeding rates in 66% of patients using Doxycycline (N=9) allowing method continuation [3, 7] Further, ours was the first US study which included women regardless of BMI (mean BMI 28.5) [3]. We further report on an expanded cohort of 337 women with an unacceptable bleeding rate of 28.5%. Where 44% of women who received Doxycycline requested removal, 92% of women who received another intervention or declined intervention requested removal. [29] With the proposed prospective randomized placebo-controlled double blinded trial , we aim to validate the implementation of a simple, affordable, non-hormonal intervention using the most rigorous methodology reported to date.

2.0 Specific Aims

2.1 Specific Aim #1 (primary aim):

- To determine the effect of Doxycycline vs. placebo on the need for additional treatment for unacceptable bleeding at 13 weeks post-randomized treatment.

2.2 Specific Aim #2 (secondary aim):

- To determine if initial treatment with Doxycycline results in higher patient satisfaction with ESI as compared to placebo at 13 weeks post-randomized treatment.

2.3 Specific Aim #3 (secondary aim):

- To determine method continuation and patient satisfaction rate at 26 week post-randomization in patients who choose secondary treatment with Doxycycline for unacceptable bleeding at 13 weeks post-randomized treatment.

In order to evaluate specific aim #1:

- All ESI patients will be offered enrollment in the study at ESI insertion and will begin prospective diaries. They will be contacted at 13 weeks post insertion. If patients report unacceptable bleeding at that time or self-report at any time following an initial 13 week interval, they will be offered randomization to Doxycycline or placebo. Patients will continue a weekly prospective symptom diary for the duration of study.
- Time to recurrence of unacceptable bleeding post-treatment and need for secondary treatment (primary endpoint) will be determined by completion of prospective symptom recording by 13 weeks post-randomized treatment.

- Side-effects and adverse events associated with medical treatment will be documented.

In order to evaluate specific aim #2:

- A patient satisfaction survey will be administered at randomization and 13 weeks post-randomization. The results will be compared between the Doxycycline and placebo study arms.

In order to evaluate specific aim #3:

- Patient satisfaction will be assessed at 13 weeks post-ESI insertion.
- Patients who report unacceptable bleeding after initial randomized treatment and who choose additional treatment will receive secondary treatment with Doxycycline and the method continuation rate and patient satisfaction rate at 26 weeks post randomization will be calculated.
- In patients who leave the study prior to 26 weeks post-randomization, patient satisfaction will be recorded at that time.
- If ESI is removed prior to 26 weeks post-enrollment, the reason, date of removal and alternative contraception will be documented.

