5.2.1 Patient selection

After appropriate IRB approval, ESI users aged 18-51 years old who meet the inclusion and exclusion criteria, and sign a written consent will be **enrolled in the study at the time of ESI insertion**. Every effort will be made to insert ESI on the same day as consent unless medically contraindicated. They will complete a prospective symptom diary from date of ESI insertion. All patients will be contacted by study personnel 13 weeks after enrollment and queried as to the presence of unacceptable bleeding. Bleeding concerns will be objectively assessed using a modification of the Pictorial Blood Loss Assessment Chart (PBLAC) [27]. Patient-initiated contact in with bleeding concerns at any time after 13 weeks post ESI insertion will result in enrollment and randomization at the time of contact. **The basis for randomized treatment will be whether or not the bleeding is “unacceptable” to the patient. This is inherently subjective, but constitutes the basis for most removal requests.** Patients who report unacceptable bleeding at 13 weeks post-ESI insertion, and those who call with bleeding concerns after 13 weeks post ESI insertion, will be randomized into two groups (Doxycycline or placebo). Patients who do not report unacceptable bleeding will continue to complete diaries and may be eligible for randomized treatment if unacceptable bleeding develops. Patients will receive diaries sufficient for completion of the study with instructions to contact study personnel if more diaries are needed or if diaries are lost. Patients and investigators will be blinded to the group assignment as well as the study coordinator who will be responsible dispensing of appropriate study medication by the pharmacy.

Patients who continue to have unacceptable bleeding after 4 weeks post-randomized treatment and wish to have secondary treatment will be treated with Doxycycline. Secondary treatment will not be blinded. Rates of unacceptable bleeding and patient satisfaction scores at 26 weeks post-randomized treatment in remaining study participants will be calculated.

[figure not shown]

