If a patient reports bleeding concerns as described in section 5.2.1 and is randomized to the placebo group, she will be given a pill bottle containing placebo made to look identical to treatment to be taken twice daily for 10 days. Patient and investigators will be blinded as to group assignment.

d. Doxycycline group

If patient has bleeding concerns determined in section 5.2.1 and is randomized to the Doxycycline group, she will be given a pill bottle containing Doxycycline 100 mg to be taken twice daily for 10 days. Patient and investigators will be blinded as to group assignment. Patients who experience unacceptable bleeding but are not bleeding at the time of study personnel contact will be instructed to call back if unacceptable bleeding recurs for randomization to treatment or placebo.

e. Treatment compliance process

Pill counts at the end of each treatment course will be performed to assess patient compliance with treatment. A pill diary given to patients at the time of randomization will provide temporal correlation between treatment initiation and bleeding symptoms.

f. Symptom recording

Upon enrollment and ESI insertion, patients will begin a weekly prospective symptom diary in order to self-assess bleeding and additional symptoms for a **total of 39 weeks from study enrollment**. A modification of the PBLAC where 1= no bleeding, 2=spotting requiring 1-2 panty-liners per 24 hours only, 3= bleeding requiring 1-3 tampons/pads in 24 hours, 4=bleeding requiring 4-6 tampons/pads per 24 hours, and 5=bleeding requiring >6 tampons/pads per 24 hours will be utilized for bleeding recording.[27] Bleeding diaries will be collected every 13 weeks and completion will be required for continued enrollment in the study and receipt of remuneration after every 13 week interval. Patients will also record any other associated symptoms such as headache, mood changes, acne and intolerance to treatment detailed in sections 6.2.2 and 6.2.3. Prospective symptom diary can be captured on a paper formate or via Mayo Clinic website RED Cap.

A bleeding episode is defined by the WHO as any set of one or more bleeding days (either consecutive or separated by only one bleeding-free day) bounded at each end by two or more bleeding-free days. **The bleeding pattern will be analyzed within each 13-week reference period** and categorized into 6 groups [4, 13, 14]:

- Amenorrhea (no bleeding during the reference period),
- Infrequent bleeding (fewer than 3 bleeding episodes),

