- Normal bleeding frequency (3-5 bleeding episodes).
- Frequent bleeding (more than 5 bleeding episodes),
- Prolonged bleeding (1 or more bleeding episodes lasting 14 days or more)

Subgroup analysis may provide additional insight into the efficacy of treatment for various bleeding patterns.

g. Patient satisfaction surveys

Patients will be asked to fill out short satisfaction surveys at randomization measuring satisfaction prior to any treatment, and at 13 and 26 weeks post randomization (see appendix). If patient has their ESI removed prior to 26 weeks post randomization, she will be given a final satisfaction survey at removal. Patient satisfaction surveys will be recorded on a paper formate or via Mayo Clinic website RED Cap.

Patients will rate their satisfaction with a) ESI and b) bleeding with ESI on a 5-point Likert scale ranging from very satisfied to very dissatisfied. If patient has ESI removed prior to 26 weeks post-study enrollment, she will be given a final satisfaction survey at removal.

h. Treatment issues

At enrollment, patients will be provided with a contact number allowing them to reach study personnel at all times with concerns. Instructions will be provided for instances of drug intolerance/allergy, heavy bleeding or other ESI related issues and clinical appointments for evaluation scheduled as needed.

i. Secondary Treatment

If a patient reports unacceptable bleeding at >4 weeks post randomization to treatment or placebo, study participation will be recorded as **need for additional treatment, and will represent the primary endpoint**. If she wishes to have secondary treatment, she will be treated with Doxycycline. Treatment will be limited to two interventions per 13 week

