5.3.2 Outcome measurements

A. Primary treatment efficacy and safety end point (primary endpoint addressing specific aim #1)

- The efficacy of Doxycycline on ESI-related bleeding will be compared to placebo based on rates of **unacceptable bleeding** and weekly prospective symptom diary at 13 weeks post-randomization.

B. Primary treatment efficacy and safety endpoints (secondary endpoints addressing specific aim #1)

- Method continuation rate at 13 weeks post-randomization will be compared for women in the Doxycycline vs. placebo group.
- Bleeding patterns will be quantified based on the PBLAC and WHO classification of clinically important bleeding patterns over each 13 week reference period.[13,14, 29].
- Incidence of additional symptoms including acne, headache, mood changes in the treatment groups will be compared to placebo at randomization and 13 weeks post-randomization based on the weekly prospective symptom diary
- Interval to recurrence of unacceptable bleeding post-randomized treatment (i.e., need for additional treatment) will be determined
- Rate of adverse events associated with medical treatment will be documented by prospective symptom diary and BMI calculation. These include headache, mood changes, acne and change in BMI.

C. Patient satisfaction with primary treatment endpoint (primary endpoint addressing specific aim #2)

- Patient satisfaction with ESI at randomization for a baseline pre-treatment satisfaction and at 13 weeks post-randomized treatment following primary treatment with Doxycycline vs. placebo will be compared

D. Patient satisfaction with secondary treatment endpoint (primary endpoint addressing specific aim #2)

- Patient satisfaction with ESI at 26 weeks post-randomized treatment for patients with continued unacceptable bleeding following primary treatment who receive secondary treatment with Doxycycline will be calculated.

E. Secondary treatment efficacy and safety endpoint (primary endpoint addressing specific aim #3)

- Method continuation rate at 26 weeks post-randomized treatment for patients with continued unacceptable bleeding after primary treatment who undergo secondary treatment with Doxycycline will be calculated

F. Secondary treatment efficacy and safety endpoint (secondary endpoints addressing specific aim #3)

- Rate of ESI removal for bleeding between 13 and 26 weeks post randomization.

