10.1.1 Remuneration

Patients will receive \$25 after each interval of 13 weeks for completion of prospective symptom diary (and pill diary if applicable) and satisfaction survey. Patients who discontinue study participation prior to completion of each 13 week set of diaries/satisfaction survey, those who do not turn in all diaries/satisfaction survey or turn in incomplete diaries/satisfaction survey will not receive this remuneration. Patients who complete the study will receive \$50.00 upon receipt of final set of diaries, satisfaction survey and study coordinator clinic visit.

[name] Investigator

- Proposal and associated material preparation
- IRB approval process
- patient consent, patient satisfaction surveys, bleeding diary preparation
- study marketing within Mayo and to MHS sites
- training and oversight of study personnel, troubleshooting
- clinical appointments for concerns
- progress report preparation
- data analysis
- manuscript preparation/submission/revision

[name]

- study marketing within Mayo and to MHS sites
- training and oversight of study personnel, troubleshooting
- clinical appointments for concerns

Study coordinator

- Patient Consent & Enrollment
- (available on-call for routine GYN clinic, scheduled for women responding to advertising)
- Available for phone contact by subjects throughout the study (triage of subject concerns)
- Phone contacts at 13 weeks for all subjects (450+)
- Clinic visits for “unacceptable bleeding” and randomization (150+)
- Phone contact at 26 weeks for all subjects
- Clinic visit at 39 weeks for all subjects

- Potential additional post-39 week phone contact for limited # subjects with late randomization
- Baseline - Consent form copying & scanning
- Baseline – data collection / case report form completion
- Subject education re: diary completion, study plan, subject responsibilities
- Collection of subject diaries at 13 – 26 – 39 weeks
- Assessing treatment compliance for randomized and secondary treatment
- Satisfaction surveys at 13 – 26 – 39 weeks
- Documentation of study participation, randomization, and follow-up in medical record
- Data entry into electronic database (clinical data, diary data, satisfaction survey data)
- Maintain subject binders / folders (150+ complex and 300+ simple)
- Organize and develop system for follow-up visits and phone calls
- Scheduling of follow-up visits (prefer to have support of the PAC office)
- Remuneration for all subjects
- Consent form development

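### No described instrument records the primary event, unacceptable bleeding after randomization, in every randomized woman at 13 weeks post-randomization

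*Combined protocol and SAP*

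**What the plan says.** Four places in the combined protocol and SAP bear on how the primary event is found.

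- **Source (2.0, evaluation of aim #1).** Time to recurrence and need for secondary treatment "will be determined by completion of prospective symptom recording by 13 weeks post-randomized treatment".
- **Outcome (5.3.2 A).** The arms are compared on rates of unacceptable bleeding "and weekly prospective symptom diary at 13 weeks post-randomization".
- **Event (5.3.1.i).** The event is recorded "If a patient reports unacceptable bleeding at >4 weeks post randomization to treatment or placebo". Whether she then wants secondary treatment is a separate step.
- **Diary (5.3.1.f).** The bleeding entry is a five-level scale of amount: "A modification of the PBLAC where 1= no bleeding, 2=spotting requiring 1-2 panty-liners per 24 hours only", and so on up to level 5. Beyond that, "Patients will also record any other associated symptoms such as headache, mood changes, acne and intolerance to treatment".

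On what counts as unacceptable, 5.2.1 leaves the judgement to the woman: "This is inherently subjective, but constitutes the basis for most removal requests".

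On staff contact, 5.2.1 says: "All patients will be contacted by study personnel 13 weeks after enrollment and queried as to the presence of unacceptable bleeding". After randomization, 5.3.1.g schedules satisfaction surveys at 13 and 26 weeks post-randomization, with one rating for the implant and one for bleeding. Section 5.3.1.j adds a staff contact at 26 weeks (±2) post-randomization for the final survey and weight. The coordinator's task list in 10.1.1 gives contacts, diary collection and surveys at 13, 26 and 39 weeks, for example "Phone contact at 26 weeks for all subjects". From the context, those weeks count from insertion.

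**The concern.** The primary event is a personal judgement, so it cannot be worked out from pad counts. Unless the diary form holds an item that the text does not describe, the source named in 2.0 cannot supply it. The event then rests on the woman contacting staff on her own initiative between week 4 and week 13 after randomization. At 13 weeks after insertion every woman is asked. At the primary time point after randomization no such question is scheduled.

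Two things are at stake. First, whether an event is recorded may depend on a woman's readiness to call as well as on her bleeding, and on how the coordinator's contacts happen to fall for her date of randomization. Second, the interval to recurrence, a secondary endpoint in 5.3.2 B, may become the date of a phone call and not the date on which bleeding became unacceptable.

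**Working it through.** **1. Does any described instrument capture the event at 13 weeks post-randomization?**

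| Instrument | Timing | Records unacceptable bleeding? | Linked to the primary event? |
|---|---|---|---|
| Diary (5.3.1.f) | Weekly | Not described; amount 1–5 and symptoms | Yes, by 2.0 and 5.3.2 A |
| Staff question (5.2.1) | 13 weeks after enrollment | Yes | No; it serves entry to randomization |
| Report by the woman (5.3.1.i) | Any time after week 4 post-randomization | Yes, if she calls | Yes |
| Survey (5.3.1.g) | 13 and 26 weeks post-randomization | No; rates satisfaction with bleeding | No |
| Staff contact (5.3.1.j) | 26 weeks post-randomization | No; survey and weight | No |

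No row is scheduled for every randomized woman at 13 weeks post-randomization, records the event, and is linked to it.

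**2. Do the coordinator's contacts fill the gap?** For a woman randomized at week w after insertion, the 26- and 39-week contacts fall at 26 − w and 39 − w weeks post-randomization.

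- w = 13: 13 and 26 weeks, matching 5.3.1.g and 5.3.1.j.
- w = 18: 8 and 21 weeks.
- w = 24: 2 and 15 weeks. The first is before an event can count and the second is after 13 weeks. Section 5.3.1.g would survey the same woman at week 24 + 13 = 37 from insertion.
- w = 26: the 39-week visit falls at 13 weeks, but 26 weeks post-randomization is week 52, beyond the fixed list. The list does allow a possible extra contact after week 39 for late randomization.

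Both post-randomization times are met only at w = 13. Later randomization is expected, since women may self-report at any time after week 13.

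**3. Power, as an illustration.** Inputs from 5.4.1: 44% on doxycycline, 80% on placebo, n = 50 per arm, two-sided chi-square test at 0.05, stated power above 90%.

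Power = Φ[(Δ − 1.96·SE₀)/SE₁], with SE₀ = √(2p̄(1 − p̄)/n) and SE₁ = √([p₁(1 − p₁) + p₂(1 − p₂)]/n).

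The plan's own figure: Δ = 0.36, p̄ = 0.62, SE₀ = √(2 × 0.62 × 0.38/50) = 0.0971, SE₁ = √((0.2464 + 0.16)/50) = 0.0902. Power = Φ[(0.36 − 0.1903)/0.0902] = Φ(1.88) = 97.0%. This agrees with the stated figure.

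Now assume that a share m of true events goes unreported, equally in both arms, and is recorded as no event. Each rate is multiplied by (1 − m).

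| m (assumed) | Doxycycline | Placebo | Difference (points) | Power |
|---|---|---|---|---|
| 0 | 44.0% | 80.0% | 36.0 | 97.0% |
| 10% | 39.6% | 72.0% | 32.4 | 91.6% |
| 20% | 35.2% | 64.0% | 28.8 | 83.2% |

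Power falls below 90% somewhere between 10% and 20% missed. The documents give no value for m.

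**The case against.** The strongest reply is that the endpoint is need for additional treatment, and 5.3.1.i makes it a report. On that reading, a woman who does not report has not met the endpoint, so nothing is missed. Every woman also has a contact number (5.3.1.h), self-report is one of the entry routes too, and section 8.1 admits the subjectivity. Taken alone, 5.3.1.i is coherent. But 2.0 takes the endpoint from the diary and 5.3.2 A asks for rates of unacceptable bleeding at 13 weeks. Neither is the same as whoever happened to call.

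The objection also limits the power figures, and this stands. Section 5.4.1 states 44% and 80% as requests for treatment, drawn from a cohort in which the figures were removal requests. Such rates already depend on women coming forward, so discounting them again may count under-reporting twice.

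Four stronger readings are tempting and are not supported:

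- A reader might infer that all fixed contacts run from insertion. Sections 5.3.1.g and 5.3.1.j run from randomization. The fault is that 10.1.1 conflicts with them.
- A reader might infer that the plan counts non-reporters as successes. No rule says so, and 5.4.2 allows time-to-event methods if follow-up becomes a problem. It is only the default result when a report-only event is compared by chi-square test in all randomized women.
- A reader might infer that the diary has no acceptability item. The form is not in the text, so only the absence of a described item is supported.
- A reader might infer bias between the arms. That would need unequal reporting, and nothing in the documents points to it: women and investigators are blinded to the randomized treatment.

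**Conclusion.** The point holds as a gap in how the primary event is ascertained. The plan describes no instrument that records unacceptable bleeding in every randomized woman at 13 weeks post-randomization. It names a diary and a self-report as sources without reconciling them, and it gives no rule for women who make no report. Ascertainment may therefore vary between women, and with time of randomization if staff follow 10.1.1.

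The size cannot be determined from the documents. The fall in power from 97% to about 92% or 83% assumes that the planning rates are rates of true events, that 10% or 20% are missed equally in both arms, and that missed events are recorded as none. The first assumption does not match 5.4.1, so the loss may be smaller. The conclusion also rests on the diary as described. If the form already asks about acceptability, what remains is to cite that item, state the classification rule and reconcile the schedules. The trial is not invalidated, but the matter should be corrected because it touches the primary endpoint and the remedy is cheap.

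**What to change.** 1. At the 13-week post-randomization survey in 5.3.1.g, ask every randomized woman the question used at entry: whether she has had unacceptable bleeding since week 4 and, if so, when it began. State in 5.3.2 A and 5.4.2 that the primary event is classified from this answer together with any earlier report. Treat a woman with no report and no 13-week answer as missing or censored, not as event-free.
2. For randomized women, reconcile the contact and survey times in 10.1.1 with 5.3.1.g and 5.3.1.j so that they run from randomization.
3. Optionally, add a weekly acceptability item to the diary as supportive data on time to recurrence. It should neither define the primary event nor change what triggers secondary treatment. Counting the first positive week as the event would redefine the endpoint and alter what prompts the unblinded treatment offer.

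The cost is one scripted question and the re-timing of contacts already budgeted. A date recalled at 13 weeks will carry some error. Somewhat more events will be recorded in both arms than from calls alone, so the text should say that the 44% and 80% planning rates were stated as requests.
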